8 ADVERSE EVENT REPORTING

It is the site's responsibility to report Adverse Events in compliance with their Institutional Review Board.

8.1 REPORTING OF ADVERSE EVENTS BY CLINICAL SITES

The following adverse events (AE) are considered reportable for this study, as determined by PI discretion:

NeuroBlate[®] System related AEs

• Adverse events related to the NeuroBlate® System Device (i.e. probe, robotic probe driver, software)

NeuroBlate[®] Procedure related AEs

 Adverse events that occur due to a NeuroBlate[®] (LITT) procedure and cannot be directly attributed to the NBS Device or surgical procedure

Surgical Procedure related AEs

• Adverse events that occur due to the surgical procedure and cannot be directly attributed to NeuroBlate[®] System or procedure (i.e. biopsy related event)

The following adverse events are considered not reportable for this registry:

- Planned hospitalization for a pre-existing condition without serious deterioration in health.
- Any expected postoperative complaints or symptoms such as pain at biopsy site, headaches, weakness, cerebral edema, and transient events (less than 30 days from procedure) that do not require intervention. If the event involves a clinically significant change in severity or duration of symptoms or requires clinical intervention that is different from ordinary postoperative care, the event is considered a reportable AE.

Reportable AEs must be described by duration (start and resolution dates), relationship to the NeuroBlate[®] System or surgical procedure, action taken to resolve the event, and outcome of the event. Additional information, such as procedural notes, treatment notes, or clinical summary may be requested as supporting documentation.

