5.1 STUDY OBJECTIVES

Objective 1: Safety

Observe safety profile described by NBS or surgical-related SAEs

Objective 2: Reason for NeuroBlate®

Objective 3: Procedural Outcomes

- Local Control
- Progression Free Survival
- Overall Survival
 - Seizure Freedom
 - Engel and ILAE Classification

Objective 4: Cognitive & Quality of Life Outcomes

Collected for subjects based on their disease etiology and age.

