8.2 ADVERSE EVENT RELATEDNESS

The relationship of the AE to the NeuroBlate[®] System Device (NBS) or the NeuroBlate[®] (LITT) procedure or surgical procedure will be determined by the Primary Investigator (PI) based upon the following definitions.

Definite: The AE follows a reasonable temporal and causative sequence from receipt (or attempted receipt) of the device treatment or procedure.

Possible: The AE follows a reasonable temporal sequence from receipt of the device treatment or procedure and the possibility of device treatment or procedure involvement cannot be excluded. However, other factors such as underlying disease, concomitant medications, or concurrent treatment are presumable.

Not Related: The AE has no temporal sequence from receipt of the device treatment or procedure, or it can be explained by other factors, including underlying disease, concomitant medication, or concurrent treatment. Note: If the event is determined to be "Not Related" to either the NBS or the Surgical Procedure, it is not considered a reportable AE.

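### Section 8.1 defines LITT-procedure and surgical AEs by mutual exclusion, so events with joint cause have no consistent category and counts by component may differ between sites

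*Protocol*

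**What the plan says.** Objective 1 (Protocol Section 5.1) is to "Observe safety profile described by NBS or surgical-related SAEs".

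Protocol Section 8.1 lists three reportable categories, to be applied at the PI's discretion:

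- **Device.** Events related to the NeuroBlate System Device ("i.e. probe, robotic probe driver, software"). There is no exclusion clause.
- **LITT procedure.** Events due to the LITT procedure that "cannot be directly attributed to the NBS Device or surgical procedure".
- **Surgical procedure.** "Adverse events that occur due to the surgical procedure and cannot be directly attributed to NeuroBlate" System or procedure.

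Section 8.1 then asks for each reportable event to be described by, among other things, its relationship to the NeuroBlate System "or surgical procedure, action taken to resolve the event, and outcome of the event". That names two sources, not three.

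Section 8.2 covers three sources: the relationship to the device, the LITT "procedure or surgical procedure will be determined by the Primary Investigator (PI) based upon the following definitions". The grades are Definite, Possible and Not Related, and nothing limits the PI to one source. Its closing note makes an event non-reportable if it is unrelated to the NBS or the surgical procedure, and does not name the LITT procedure.

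Section 8.3 provides third-party adjudication of reported events for publications. Section 10 is descriptive, with no hypothesis. The SAP (Comparative Analysis) permits, but does not require, comparisons of survival or event rates by disease state, demographics, product model or other factors.

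**The concern.** Surgical access and ablation are steps of one operation: Section 3 describes a hole made in the skull and a probe then used to heat tissue. Section 8.1 itself mentions weakness and cerebral edema, which become reportable when they go beyond ordinary postoperative care. A PI may reasonably judge that both steps caused such an event, and Section 8.1 gives no combined category, tie-break or residual class for it.

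Safety is the first objective, and the definitions are applied separately at up to 50 sites. If one site books a joint event as LITT-related, another as surgical, another as both, and another leaves it out because neither definition fits, the component counts do not measure the same thing across sites. A product-model comparison that used those counts would inherit the problem. Adjudication under Section 8.3 sees only what sites report, and no attribution rule is given for it.

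**Working it through.** The plan states no SAE rate, sample-size calculation or error rate on this point, so there is no figure to reproduce. The check is logical.

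**Step 1: literal reading.** Let D, L and S stand for device, LITT procedure and surgery, and read caused by as directly attributable to. Three sources give 2³ − 1 = 7 combinations.

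| Cause | Device | LITT | Surgical | Result |
|---|---|---|---|---|
| D | yes | – | – | device |
| L | – | yes | – | LITT |
| S | – | – | yes | surgical |
| D+L | yes | excluded | – | device only |
| D+S | yes | – | excluded | device only |
| D+L+S | yes | excluded | excluded | device only |
| L+S | – | excluded | excluded | **none** |

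One of seven combinations has no category. L appears in four combinations, and only one (L alone) enters the LITT count. The same holds for S and the surgical count.

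**Step 2: the word directly.** Suppose an event is due to both L and S, but the PI cannot attribute it directly to either. Neither exclusion then applies, and the event satisfies the LITT and surgical definitions together. The same clinical picture can therefore fit no category or two, depending on how the PI reads one adverb.

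**Step 3: effect on the counts.** Let n_L and n_S be the events due to L alone and S alone, n_LS the events due to L+S without the device, and N all related events. Of the n_LS events, let fractions a, b, c and d be booked as LITT only, surgical only, both, and neither, with a + b + c + d = 1. If device-shared events are classified as in Step 1:

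- LITT count = n_L + (a + c) × n_LS
- Surgical count = n_S + (b + c) × n_LS
- Any-related total, each event counted once = N − d × n_LS

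The total depends only on d. If sites report every joint event, d = 0 and the total is N, however the events are divided. The component counts depend on a, b and c, which the protocol leaves open and which may differ by site. The documents give neither n_LS nor any of the fractions, so no size follows.

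**Step 4: which sources each passage names.**

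| Place | Device / NBS | LITT procedure | Surgery |
|---|---|---|---|
| 5.1 Objective 1 | yes | not named | yes |
| 8.1 categories | yes | yes | yes |
| 8.1 relationship description | yes | not named | yes |
| 8.2 assessment | yes | yes | yes |
| 8.2 Not Related note | yes | not named | yes |

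The abbreviation list gives NBS as the whole system, while Section 8.2 attaches it to the System Device. Whether NBS includes the LITT procedure in the three places where that procedure is not named is therefore unclear. If NBS means the device alone, an event due only to the LITT procedure is reportable under 8.1 and non-reportable under the 8.2 note.

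**The case against.** The case for leaving the text alone has several sound parts.

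- **Device-shared events are not lost.** A reader might infer that any event shared with the device also fits no category. It does not follow: the device category has no exclusion, so D+L, D+S and D+L+S are all captured. What remains is that they leave the LITT and surgical counts.
- **No NBS-versus-surgical comparison is planned.** A reader might conclude that such a split is invalid. Objective 1 joins the two with or and reads as a union, and neither Section 10 nor the SAP compares SAEs by attribution. The supportable statement is that component counts are not consistently defined.
- **Loss of joint events is not shown.** The 8.2 note removes only events judged Not Related, and a jointly caused event is related. The non-reportable list in 8.1 does not name such events either. Omission is a risk under a literal reading of 8.1, so a claim of downward bias would go beyond the documents.
- **The size is unknown.** One could assume an SAE rate and a joint-cause share and multiply by 3,000. The documents give neither rate, and 3,000 is an enrollment ceiling.
- **Partial remedies exist.** Section 8.2 already refers to three sources, the eCRF is not among the documents and may already record them separately, and Section 8.3 adds adjudication. The competing causes named under Possible are disease, medication and concurrent treatment, so that grade was not plainly written for two steps of one operation.

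These points narrow the concern but do not remove it. Sections 8.1 and 8.2 still give different rules for the same event, and adjudication cannot recover an event that a site did not submit.

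**Conclusion.** The concern holds in a limited form. The LITT and surgical definitions exclude each other, so an L+S event without a device role meets neither when it is directly attributable to both, and meets both when it is directly attributable to neither. That is a defect in a stated data-collection rule, more than a missing detail.

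The consequence is inconsistent component counts between sites and, on a literal reading, possible omission of joint events. The all-related total stands if sites report those events. The effect cannot be sized from the documents. The conclusion assumes that joint ablation-and-access events occur and that component counts will be tabulated or used in one of the SAP's optional comparisons. The change should be made because it is cheap and unreported events are hard to recover later.

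**What to change.** 1. Delete the two exclusion clauses from the LITT-procedure and surgical-procedure definitions in Section 8.1.
2. Have the PI grade every AE Definite, Possible or Not Related three times: for device, LITT procedure and surgical procedure.
3. Make an AE reportable, subject to the existing list of non-reportable events, if any of the three grades is Definite or Possible.
4. Name all three sources in the 8.1 relationship description, the 8.2 Not Related note and Objective 1, and define NBS once.
5. State in the SAP that SAEs are reported by component with overlap allowed, plus one any-related total counted once per subject.

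The cost is protocol wording and possibly a change to the relatedness fields. Component counts will no longer add to the total, which needs a footnote in each safety table.

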Karnofsky Performance Scale (KPS)	 The KPS will be collected for brain malignancy subjects only, and for subjects 16 years and older. The scale runs from 100 to 0, where 100 is "perfect" health and 0 is death: 100 - Normal; no complaints; no evidence of disease. 90 - Able to carry on normal activity; minor signs or symptoms of disease. 80 - Normal activity with effort; some signs or symptoms of disease. 70 - Cares for self; unable to carry on normal activity or to do active work. 60 - Requires occasional assistance but is able to care for most of his personal needs. 50 - Requires considerable assistance and frequent medical care. 40 - Disabled; requires special care and assistance. 30 - Severely disabled; hospital admission is indicated although death not imminent. 20 - Very sick; hospital admission necessary; active supportive treatment necessary. 10 - Moribund; fatal processes progressing rapidly. 0 - Dead
Lansky Performance Scale (LPS)	The LPS will be collected for brain malignancy subjects only, and for subjects between 1 year and 16 years of age. The scale runs from 100 to 0, where 100 is "perfect" health and 0 is death: 100 – Fully active, normal 90 – Minor restrictions in strenuous physical activity 80 – Active, but gets tired more quickly 70 – Greater restriction of play and less time spent in play activity 60 – up and around, but active play minimal; keeps busy by being involved in quieter activities 50 – Lying around much of the day, but gets dressed; no active playing participates in all quiet play and activities 40 – Mainly in bed; participates in quiet activities 30 – Bedbound; needing assistance even for quiet play 20 – Sleeping often; play entirely limited to very passive activities 10 – Doesn't play; does not get out of bed 0 – Unresponsive
Serious Adverse Event (SAE)	 Adverse Event that: (a) Led to death (b) Led to serious deterioration in the health of the subject, that either resulted in life-threatening illness or injury A permanent impairment of a body structure or a body function In-patient or prolongation of existing hospitalization Medical or surgical intervention to prevent permanent impairment to a body structure or a body function (c) Led to fetal distress, fetal death or a congenital abnormality or birth defect

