15 INVESTIGATOR REPORTS AND RECORDS REQUIREMENTS

The Investigator is responsible for the completion and submission to the Sponsor of all CRFs, AEs or other reportable study events (e.g. procedure related complications), and deviations from the protocol. If any action is taken by an IRB with respect to the study, the information must be forwarded to the Sponsor in a timely manner.

The Investigator shall prepare and submit complete, accurate, and in a timely manner, the reports listed in Table 2 below. In addition to this list, individual IRBs may add additional requirements and/or require a different notification time frame.

. -

-

Type of Report	Notification prepared by Investigator for	Notification Time Frame		
Reportable Serious Adverse Events as Described in Section 8	Sponsor	As soon as possible, preferably		
Death or Serious Adverse Event	IRB per policy	within 48 hours after discovery of event.		
Withdrawal of IRB Approval	Sponsor	Within five (5) working days.		
Deviations to the Protocol	Sponsor IRB per policy	As soon as possible after occurrence of deviation.		

All data must be stored and retained by the investigative site for a minimum of 2 years following a notification from Sponsor that all investigative sites are complete, terminated, or discontinued. Should the investigator withdraw from the responsibility of retaining study records, then custody of the records transfers to a person assuming responsibility. Sponsor will be notified in writing of new custodian by the investigative site.

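### The Section 8.1 reporting exclusion is not tied to the protocol's SAE definition, so some related SAEs can go unreported and Objective 1 can be understated

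*Protocol*

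**What the plan says.** Protocol Section 5.1 gives the safety objective as: "Observe safety profile described by NBS or surgical-related SAEs".

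Protocol Section 1 defines an SAE. Apart from death and fetal or congenital harm, an event is serious when it causes a serious decline in health with one of four results. Two of these matter here: "In-patient or prolongation of existing hospitalization" and "Medical or surgical intervention to prevent permanent impairment to a body structure or a body function". Neither makes an exception for expected events or for routine management.

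Protocol Section 8.1 leaves reportability to the discretion of the site's Primary Investigator (PI) and lists what is not reportable. The second item covers "expected postoperative complaints or symptoms such as pain at biopsy site, headaches, weakness, cerebral edema, and transient events (less than 30 days" from the procedure). It continues: "that do not require intervention. If the event involves a clinically significant change in severity or duration of symptoms", or if it "requires clinical intervention that is different from ordinary postoperative care, the event is considered a reportable AE".

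In Protocol Section 15, Table 2 sends to the sponsor "Reportable Serious Adverse Events as Described in Section 8". Under Section 8.3, the Safety Committee adjudicates the events that were reported.

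The SAP has no separate safety section. It summarises categorical data by count and percentage, and it allows event rates to be compared between subgroups, including disease states and product models.

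**The concern.** The safety objective is defined by seriousness. The filter that decides what enters the safety data is defined by expectedness, duration and type of management. Unless the two are linked, an event can meet the SAE definition and still be screened out before it is recorded as an SAE.

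The exclusion names weakness and cerebral edema, which are neurological consequences of treating brain tissue and so are central to a device safety profile. An event that never reaches an AE form cannot be restored at analysis; it would have to be found again by source review. Omission can only lower the SAE count. The decision rests with individual PIs at up to 50 sites, so capture could also differ between sites and disturb the subgroup and product-model comparisons that the SAP allows.

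**Working it through.** No arithmetic applies. The documents give no SAE rate, sample-size calculation or hypothesis for safety. The check sets each SAE criterion in Section 1 against the conditions in Section 8.1 that make an excluded event reportable again.

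1. **Death or life-threatening illness.** Section 8.1 does not name these, but either would in practice be a clinically important change in severity. Recovered.
2. **Permanent impairment**, such as weakness that persists. The severity or duration condition probably recovers it. Some judgement remains, because the protocol sets no expected duration to measure a change against. Mostly recovered.
3. **Intervention to prevent permanent impairment.** Recovered if the intervention goes beyond ordinary postoperative care. If the PI regards it as ordinary care, the two sentences of Section 8.1 give different thresholds. The first limits the exclusion to events needing no intervention at all. The second brings back only events needing non-routine intervention. An event managed with routine intervention lies between them, and sites can read it either way. Partly open.
4. **In-patient or prolonged hospitalization.** Neither condition mentions hospitalization. Suppose edema or transient weakness amounts to a serious decline in health and lengthens the stay, and the PI judges its course to be within what was expected. If it needs no non-routine intervention, no condition expressly makes it reportable. Open.

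The wording leaves a further ambiguity: the no-intervention limit may govern the whole list or only the transient events. If it governs only the latter, expected weakness and edema are limited by the second sentence alone, and the gap in item 3 widens. Item 4 stays open on either reading.

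The other exclusion in Section 8.1 makes a useful contrast. Planned hospitalization is excluded only when there is no serious decline in health. The expected-symptoms item has no such qualifier.

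The last step is to look for another route into the SAE data:

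- Table 2 limits sponsor notification to SAEs that are reportable under Section 8.
- Section 8.3 covers reported events.
- Section 14 asks for AE documentation only for protocol-reportable events.
- The opening of Section 15 speaks more generally of submitting AEs and other reportable events, but it does not set aside the list in Section 8.1.

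No stated route recovers an SAE that has been screened out at Section 8.1.

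**The case against.** The strongest reply is that Section 8.1 already has a working safeguard. Hospitalization counts as serious only within a serious decline in health, and a PI who sees such a decline would ordinarily also see a clinically important change in severity. On that view nearly every true SAE returns. This stands for fatal, life-threatening and most permanent events. It does not settle the other two criteria, because the link is left to inference and to each PI.

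A reader might infer that any longer stay is an SAE under Section 1, or that serious weakness and edema are dropped as a rule. The documents support neither. A longer stay without serious decline does not meet the definition, and the re-entry conditions are real. The supportable statement is that some SAEs can be missed.

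A reader might also see a conflict between the 30-day transience wording and the reporting time in Table 2. That is not established. The table states 48 hours as a preference, severity and need for intervention can be judged at discovery, and it is unclear whether the 30 days applies to the whole list.

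It can fairly be added that the registry is descriptive, so no test or decision rule depends on this. Neurological exam, gait and medication data are also collected at discharge and follow-up, and Table 2 lists deaths and SAEs for the IRB, per its policy, without the reportable qualifier. These points limit the consequence, but none of these records feeds the registry's SAE count.

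**Conclusion.** The point holds in a limited form. Section 8.1 is not tied to the Section 1 SAE definition. Its re-entry conditions recover most serious events. They do not expressly recover those that are serious through in-patient or prolonged hospitalization, or through preventive intervention that the PI treats as ordinary care. Such events can go unreported, and the Objective 1 profile can then be understated and can vary by site.

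The size cannot be estimated. The documents give no rate of such events, no reported SAE rate, and no indication of how PIs apply the conditions. A percentage or a count of missed subjects would have no basis in them.

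The conclusion assumes that sites follow Section 8.1 as written and that no instruction outside these documents, such as CRF guidance, closes the gap. The direction of any error follows from the rule, since leaving events out can only reduce the count. Variation between sites is a possibility created by PI discretion; the documents do not show that it occurs.

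**What to change.** Reconcile Section 8.1 with Section 1 and Objective 1. Add to Section 8.1 that the non-reportable categories apply only to non-serious events, and that any device-, LITT- or surgical-procedure-related event meeting the Section 1 SAE definition is reportable, whether or not it was expected, transient or managed with ordinary postoperative care. This changes what is recorded and leaves patient management as it is. Table 2 and Section 8.3 then work without amendment, because both depend on what Section 8 makes reportable.

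If the sponsor prefers to keep the present rule, Objective 1 and any publication of the SAE profile should state that these events are not fully captured.

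The cost is one or two sentences of protocol text, site retraining and some additional AE forms. The published SAE rate may be less favourable. Events already screened out would stay missing unless source records were reviewed, so reports that pool data from before and after the change should say so.
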